# I. BACKGROUND AND SIGNIFICANCE

Autism Spectrum Disorder (ASD) is a common, childhood-onset, lifelong neurodevelopmental disorder characterized by persistent deficits in social communication and social interaction as well as restricted interests and activities (American Psychiatric Association, DSM 5). Individuals with ASD frequently struggle with cognitive inflexibility and non-verbal learning disability (NVLD), which can compound the clinical picture. It is estimated that up to 1% of children are affected with ASD and more than half of them have adequate cognitive and language abilities (hence "high functioning" [HF]) Such HF-ASD individuals can more successfully participate in educational programs and achieve adequate educational skills that could facilitate them joining the workforce and attain independence . Although a key factor towards attaining independence is the ability to drive , recent estimates indicate that only one-third of individuals with HF-ASD drive , a much lower rate that non-affected youth. This finding suggests that driving may pose unique challenges to individuals with HF-ASD.

Although the reasons for driving challenges in individuals with HF-ASD remain unclear, findings from a recent pilot driving simulation study  in HF-ASD drivers suggested that anxiety could be an important contributor. In that study, during the driving simulation, drivers with HF-ASD manifested significantly abnormalities in gaze directionality relative to controls as well as elevated heart rates and abnormal skin conductance relative to controls. Because these physiological correlates are well-known proxies for hyperarousal and anxiety, these findings raise the possibility that driving induces hyperarousal and anxiety in this population that could lead to the abnormalities in atypical eye tracking behaviors observed. These findings raise the possibility that if driving induced anxiety could be mitigated, it could improve driving performance of HF–ASD individuals.

One such intervention is the atypical anxiolytic medicine busporine. Unlike other anxiolytics, the pharmacology of buspirone is not related to that of benzodiazepines, barbituates or carbamates (it is not a GABA receptor agonist) and so buspirone does not carry abuse potential risk for which other anxiolytics are known. As such, buspirone is not considered to be a drug-of-abuse and is unscheduled. Buspirone is rapidly acting and non-sedating. It is also a very safe medicine with a benign adverse effect profile, no meaningful drug-drug interactions, and lacks withdrawal reactions. Because of its short duration of action, it can be used on as needed basis making it an ideal and safe compound to target driving-induced anxiety in HF-ASD individuals. The main aim of the current study is to test the hypothesis that pharmacological pre-treatment (2 days before and during the simulation) of adult drivers with HF-ASD with low doses of buspirone (5.0 mg BID) will be associated with reduction in hyperarousal as measured by elevated heart rates and abnormal skin conductance, and improvement in driving performance in a simulator as measured by eye tracking deviations. To this end, we propose to conduct a randomized cross-over trial of treatment with buspirone for 2 days before and during the simulation in 24 HF-ASD subjects using an AB-BA design.

## II. SPECIFIC AIMS

Main Aim: To examine the effects of treatment with the anti-anxiety medicine buspirone on driving performance (eye tracking) in individuals with HF-ASD.

**Hypothesis:** We hypothesize that, compared to the untreated performance, treatment with buspirone will improve 1) physiologically measured hyperarousal (through heart rate and skin conductance) and 2) driving performance (eye tracking deviations) while performing a simulated driving task in a driving simulator.

## III. SUBJECT ENROLLMENT

We propose to enroll 24 adult drivers with HF-ASD. Subjects will be males and females, ages 18-45, with a diagnosis of DSM-V Autism Spectrum Disorder. Potential subjects will be recruited from advertising in the local media (newspapers, radio, etc.), MBTA advertisements, flyers posted in the local community and on college campuses, and through the MGH recruitment website, Rally. Potential subjects may also be recruited from local associations that provide programming for individuals with HF-Autism Spectrum Disorder (e.g. AANE, Aspire) or through outpatient clinics at MGH that service individuals with HF-ASD. If a potential subject expresses interest to participate in the study via email, the coordinator will reply and instruct the subject to review the Partner's required language surrounding encrypted and unencrypted emails and will verify their preference prior to proceeding with email communication.

A brief phone screen will be completed with subjects who are interested in participating in the study by a member of study staff. The phone screen asks some questions regarding medical and psychiatric history. If the subject is eligible after the screen, a member of study staff will schedule a time for them to come into the office.

Informed consent will be obtained by a licensed physician investigator prior to the performance of any study procedures. The informed consent will be used to explain, in simple terms, the risks and benefits of study participation to the subject. The subjects may take as much time as they feel necessary to consider their participation in the study, as well as consult with their family members or a physician.

## **Inclusion Criteria:**

- Males and females, ages 18-45, with a diagnosis of DSM-V Autism Spectrum Disorder
- Has a valid Driver's License or a current state-issued driving permit who are actively driving, as deemed appropriate by the investigator

## **Exclusion Criteria:**

- Major sensorimotor handicaps (e.g. deafness, blindness)
- Individuals who have never held a valid driver's license or a current state-issued driving permit
- Intellectual Deficiency (Verbal Comprehension Index < 80)
- Inadequate command of the English language

- Subjects with any clinically meaningful medical or psychiatric condition as determined by the investigator
- Individuals who are currently taking a monoamine oxidase inhibitor (MAOI) for any reason
- Pregnant

### IV. STUDY PROCEDURES

Completion of this study will be dependent on the availability of the participant and includes a clinical assessment visit at Massachusetts General Hospital and two driving simulation visits (approximately 1.5 hours each) at Massachusetts Institute of Technology.

### Assessment Visit

Before any study procedures are initiated, subjects will provide informed consent. The informed consent documents will be used to explain in simple terms the risks and benefits of study participation. The nature of the study will be fully explained to the subject by a board-certified physician who is either the primary investigator or a co-investigator. The subject will be encouraged to ask questions pertaining to their participation in the study, and the subject may take as much time as they feel necessary to consider their participation in the study. Participation in this study is voluntary, and the subject may withdraw at any time for any reason. The IRB-approved informed consent documents will be signed and dated by the subject and the physician obtaining consent.

After providing informed consent, if a subject has been previously diagnosed with a DSM Autism Spectrum Disorder by a licensed psychiatrist and documentation of that diagnosis is available then the K-SADS direct and indirect interviews will be bypassed. Otherwise, all subjects will be interviewed by a licensed physician or psychologist to confirm the DSM-V diagnosis of Autism Spectrum Disorder. The interview will use the questions and probes from the Kiddie Schedule for Affective Disorders and Schizophrenia (K-SADS-PL) model on ASD. Because the K-SADS-PL was designed for use in clinical and epidemiological research to obtain past and current history of psychiatric disorders in children and adolescents aged 6 to 17, it will be adapted to be used as a direct interview with adults with suspected ASD. Whenever the direct assessment for the diagnosis of ASD with the subject is unclear, if possible and feasible, an additional indirect interview will be conducted with a parent as informant. The subject must grant permission for the research team to contact a parent for the indirect interview. If they agree, the parent will be contacted via telephone. Interviews can be done in person, via telephone, or via telemedicine through the MGH secure site based on subject preference. The subject's responses will be recorded on paper and entered in RedCap by the clinician or a member of study staff. If both a direct and indirect interview are completed for a participant the we will combine data by considering a diagnostic criterion positive if it was endorsed in either interview.

Subjects will also be asked to complete the Adult Self Report (ASR), a 126-item self-report questionnaire that assesses aspects of adaptive functioning and problems, and asks individuals to rate items on a 3-point scale (0-Not True, 1-Somewhat or Sometimes True, 2-Very True or Often

True). Subjects will have a choice to complete this instruments remotely through a RedCap secured link or in person. RedCap is a platform for electronic data capture that streamlines data collection and management, and ensures data integrity, resulting in improved data quality. If RedCap is unavailable for use, the subject will complete the ASR on paper and it will later be entered into RedCap by a member of study staff.

In addition, we may ask a parent, guardian, or third-party informant to complete the Adult Behavior Checklist (ABCL). The ABCL is an informant version of the ASR that assesses similar aspects of adaptive functioning and problems, and asks informants to rate items on a 3-point scale (0- Not True, 1- Somewhat or Sometimes True, 2- Very True or Often True). If this is the case, the subject must grant permission for the research team to contact a parent, guardian, or third-party informant for the completion of this questionnaire. If the participant agrees, this instrument will be provided to the informant through a Redcap secured link or in person. If RedCap is unavailable for use, the informant will complete the ABCL on paper and the data will be entered into RedCap by a member of the study staff. This questionnaire will either be used instead of the ASR or to supplement the provided answers on the ASR.

Each subject will be compensated \$90.00 in the form of a check for completing the MGH Assessment Visit.

## **Driving Simulation Visits**

Previous work between MGH and MIT utilized the simulator that will be used in this study . After completion of the Assessment Visit, the subject will schedule the two driving simulation visits at Massachusetts Institute of Technology during this time they will be given or emailed an information sheet regarding what the MIT driving simulation visit will entail. Each driving simulation visit will be approximately 1.5 hours long. At the first driving simulation visit, subjects will be asked to review and sign the MIT consent form before proceeding.

Half of eligible and consenting subjects (A-B group) will be tested on the driving first on medication while the other half (B-A group) will be tested first unmedicated based on a randomization list. The subjects will be instructed to take 5.0 mg of buspirone with breakfast and 5.0mg of buspirone with dinner for 2 days before their driving simulation. On the day of the simulation, they will be instructed to take the dose 1 hour before the simulation. A member of study staff will remind the subjects via phone call and/or email to take their medication on the two days preceding their driving simulation, and remind them of the specific times at which they should take the medication.

If a subject is assigned to the A-B group per the randomization list, they will receive the buspirone at the completion of their assessment visit at MGH. A member of study staff will remind the subject that they should not take the medication until 2 days before the driving simulation. Written instructions will also be provided explaining the dates and times when the medication should be taken. If the individual is currently taking buspirone they will be instructed to take the busiprone, as prescribed, prior to their first simulation visit. However, prior to their second simulation visit with MIT they will be asked to withhold their medication starting 24 hours prior to their second visit.

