#### Improving Driving in Adults with Autism Spectrum Disorders PI: [name]

The other half of the eligible and consenting subjects (B-A group), per the randomization list, will take the buspirone the two days preceding their second driving simulation, and on the day of their second driving simulation at MIT. On the day of their first scheduled driving simulation visit at MIT, a member of study staff from MGH will meet the subject at MIT. After the first driving simulation is complete, the member of study staff will provide the subject with the buspirone, and instruct the subject that he/she should take the medication for two days preceding their second scheduled driving visit, and the day of their second scheduled driving visit. The member of study staff will also provide the subject with written instructions of the dates and times when the medication should be taken, and send a reminder to the subject via phone call or email. If the individual is currently taking buspirone, they will be instructed to withhold their medication starting 24 hours prior to their first visit and then take the buspirone, as prescribed, prior to their second visit. If the member of study staff from MGH is unable to attend the subject's first driving simulation visit at MIT, the prescription of buspirone will be picked up from the Clinical Trials Pharmacy, and the research coordinator will package the medication. The medication will be shipped to the subject using UPS. The subject will be notified on which day they should expect to receive the medication, and that they will need to sign for the delivery. The package will include dosing instructions for the medication and will indicate which dates the medication should be taken based on when their driving simulation visit at MIT is scheduled.

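### The AB-BA crossover sets no interval between the two drives, so for subjects given study drug the minimum gap differs by sequence and only existing buspirone users have a stated off-drug period

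*Combined protocol and SAP*

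**What the plan says.** Section I describes treatment "for 2 days before and during the simulation in 24 HF-ASD subjects using an AB-BA design". Under Driving Simulation Visits, "Half of eligible and consenting subjects (A-B group) will be tested on the driving first on medication"; the other half are tested unmedicated first.

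**Interval.** Section IV says "Completion of this study will be dependent on the availability of the participant", and under Driving Simulation Visits "the subject will schedule the two driving simulation visits at Massachusetts Institute of Technology". No minimum, maximum or target interval between the two drives is given anywhere.

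**Subjects given study drug.** For the medicated drive, "On the day of the simulation, they will be instructed to take the dose 1 hour before the simulation". In A-B that is the first drive, and no length of time off drug is stated before the second. In B-A the drug is handed over after the first drive, or shipped, and the subject "will take the buspirone the two days preceding their second driving simulation". Two dosing days therefore lie between the drives.

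**Subjects already taking buspirone.** In A-B, before the unmedicated drive, "they will be asked to withhold their medication starting 24 hours prior to their second visit". A matching 24-hour hold precedes the first drive in B-A. These B-A subjects then take their own drug as prescribed, so the two-dosing-day gap does not apply to them.

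**Analysis.** Section V specifies GEE models with robust variance. It names no period, sequence or carryover term.

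**The concern.** A 2x2 crossover estimates the treatment effect without bias only if nothing from the first drive affects the second differently in the two sequences. Two routes are open here.

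- **Residual drug.** If an A-B subject's second drive comes soon after the first, some drug effect may remain in what is analysed as the untreated condition.
- **Practice.** The second drive benefits from having done the first. If the time between drives differs by sequence, the gain kept may differ too.

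Both are confounded with treatment. The interval is the design feature that controls them, and the plan leaves it to scheduling, with a different floor in each sequence for subjects given study drug.

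**Working it through.** The plan gives no power calculation, effect size, SD or within-subject correlation, so it has no figure of its own to reproduce. The inputs from the documents are 24 subjects, half per sequence (12 and 12 if all complete). Every other value below is an assumption.

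**1. What the contrast estimates.** Let tau be the true drug effect, lambda the residual drug effect in the A-B second drive, and pi_AB and pi_BA the practice gains from drive 1 to drive 2.

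| Sequence | Drive 1 | Drive 2 | Medicated minus unmedicated |
|---|---|---|---|
| A-B | tau | pi_AB + lambda | tau - pi_AB - lambda |
| B-A | 0 | tau + pi_BA | tau + pi_BA |

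The period-adjusted estimate is the average of the last column:

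tau - lambda/2 + (pi_BA - pi_AB)/2.

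If lambda = 0 and the practice gains are equal, it equals tau. Otherwise the bias stays, although a period term is already in the model.

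**2. Carryover (assumed).** With lambda = c × tau and equal practice gains, the estimate is tau(1 - c/2). For c = 10%, 25% and 50% this is 0.95, 0.875 and 0.75 of tau, so 5%, 12.5% and 25% too small.

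**3. How plausible is c?** The documents give no half-life. If the effect decays with half-life h, the share left after t hours is 2^(-t/h).

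| Assumed h | Left after 2 h | Left after 24 h |
|---|---|---|
| 3 h | 63% | 0.4% |
| 6 h | 79% | 6% |
| 12 h | 89% | 25% |
| 24 h | 94% | 50% |

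With h of 3 to 6 hours and a one-day gap, the estimate shrinks by about 0.2% to 3%. Larger losses need drives very close together or a longer-lasting effect.

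**4. Unequal practice (assumed).** With pi_AB = 0.4 SD and pi_BA = 0.2 SD, the bias is (0.2 - 0.4)/2 = -0.10 SD. Reversing the two gives +0.10 SD.

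**5. Effect on the test (simulated).** Assumptions: SD 1, visit correlation 0.5, tau = 0.6 SD, 12 per sequence, two-sided 5% test on 22 df, 20,000 replicates. Power is 79.7% with no carryover, 69.3% at 25% and 55.6% at 50%. With tau = 0 and a practice difference of 0.3 SD in either direction, the type I error is about 11%.

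**6. Could the data reveal it?** The sequence test compares subject totals between sequences. For lambda = 0.3 SD and correlation 0.5, the standard error is sqrt(2 × 1.5) × sqrt(2/12) = 1.732 × 0.408 = 0.707 SD. The ratio is 0.3/0.707 = 0.42, which gives about 7% power on 22 df. A correlation of 0.7 gives sqrt(2 × 1.7) × 0.408 = 0.753 SD and again about 7%.

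**7. No period term.** An equal practice gain cancels at 12/12 without a period term, but not after uneven dropout. With tau = 1, a gain of 0.5 and 12/9 completers, the unadjusted estimate is (12 × 0.5 + 9 × 1.5)/21 = 0.929. With a period term it is 1.000.

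**The case against.** The strongest reply is that little may go wrong in practice. The drives are separate visits of about 1.5 hours each. A-B subjects get written dosing dates and times tied to the first drive, and no study dose is scheduled after it, so the time between visits is off drug. Section I calls buspirone short-acting, and the protocol applies a 24-hour hold to regular users. An adaptation drive of about 10 minutes is meant to reduce novelty. Participant availability will drive the interval in both sequences, and nothing shows that actual intervals would differ on average.

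Much of this stands. A reader might infer that A-B subjects have no off-drug period at all. The documents do not support that: existing users have a stated 24-hour hold, and for the others what is missing is a minimum length. A reader might also infer that carryover could produce a false benefit. Residual drug acting in the same direction as the drug pulls the estimate toward no benefit. So would a larger practice gain in A-B after a shorter gap. A false benefit needs the larger practice gain in B-A.

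The gap in the plan itself is not answered. A short duration of action protects only if some interval is assured, and for A-B subjects given study drug none is. It does not bear on practice. The adaptation drive is brief next to a main drive of about 45 minutes, and the protocol says only that it reduces novelty.

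**Conclusion.** The point holds as a design gap. For subjects given study drug, the plan builds in two dosing days between drives in B-A and no minimum in A-B. The one off-drug rule covers only existing users, to whom the B-A gap does not apply. The plan therefore allows residual drug at the A-B unmedicated drive and intervals that differ by randomised sequence. Either would bias the treatment contrast in a way that a period term cannot remove and a trial of 24 cannot diagnose.

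The size is unknown. The percentages and SD shifts above rest on assumed carryover, practice, half-life, SD and correlation, and show scale only. If visits fall at least a day apart and the drug is as short-acting as Section I says, carryover would be small. The documents do not support reading this as proof that the result will be biased: unequal intervals are permitted, not shown. The change is worth making because it is cheap beforehand and the problem cannot be repaired afterwards.

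**What to change.** In Section IV:

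- Apply one inter-visit interval rule to both sequences, with a minimum and a target window. A shared minimum alone would not equalise the intervals above it.
- Reconcile the off-drug condition before the unmedicated drive across subjects given study drug and subjects already taking buspirone. The investigator sets all lengths; none is proposed here.
- Record the date and time of each drive and of the last dose before it, so that actual intervals can be reported by sequence.

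In Section V, include a period term in the GEE model. It will not cure carryover or unequal practice, but it removes a common practice effect when the sequences end up unequal in size.

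The cost is a few sentences and slightly less scheduling freedom. No visits, subjects or procedures are added.

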#### Improving Driving in Adults with Autism Spectrum Disorders PI: [name]

The other half of the eligible and consenting subjects (B-A group), per the randomization list, will take the buspirone the two days preceding their second driving simulation, and on the day of their second driving simulation at MIT. On the day of their first scheduled driving simulation visit at MIT, a member of study staff from MGH will meet the subject at MIT. After the first driving simulation is complete, the member of study staff will provide the subject with the buspirone, and instruct the subject that he/she should take the medication for two days preceding their second scheduled driving visit, and the day of their second scheduled driving visit. The member of study staff will also provide the subject with written instructions of the dates and times when the medication should be taken, and send a reminder to the subject via phone call or email. If the individual is currently taking buspirone, they will be instructed to withhold their medication starting 24 hours prior to their first visit and then take the buspirone, as prescribed, prior to their second visit. If the member of study staff from MGH is unable to attend the subject's first driving simulation visit at MIT, the prescription of buspirone will be picked up from the Clinical Trials Pharmacy, and the research coordinator will package the medication. The medication will be shipped to the subject using UPS. The subject will be notified on which day they should expect to receive the medication, and that they will need to sign for the delivery. The package will include dosing instructions for the medication and will indicate which dates the medication should be taken based on when their driving simulation visit at MIT is scheduled.

MIT AgeLab driving simulation experiments are conducted in a high fidelity driving simulator designed and fabricated by RTI (Realtime Technologies Inc., Ann Arbor, MI), running the SimCreator and SimVista software packages. The simulator consists of the full cab of a 2001Volkswagen New Beetle. Three exterior screens provide a 180-degree simulated forward and partial side field of view of a virtual roadway and associated environment. A rear projector screen behind the car displays the rear roadway, which is viewable using the vehicle's standard rearview mirror. Two LCD displays placed in the cab's side mirrors present images of the rear roadway in a perspective corresponding to what actual side mirrors provide. Images of the roadway are displayed at 60 frames per second. The steering wheel, accelerator, and brake pedals all provide force feedback to the subjects. Internal and external speakers produce simulated vehicle and environmental sound during the experiment. The cab is instrumented with three cameras and one microphone to record the environment in the cab. One camera is focused on the driver's face to capture head and eye movements, one is positioned to recorded hand movements and interactions with steering wheel and center stack, and the final camera is positioned to record the forward screen to validate video and simulator data synchronization. The simulator is also instrumented with the capacity to record from a wide variety of physiological sensors using medical grade instrumentation (FDA 510(k) reviewed class II) (NeuroDyne Medical Corp., model MEDAC System/3) to monitor changes in a subject's internal state (sensors to be used are detailed below) associated with the environmental stimulation of the virtual roadway and the driving task.

Upon reporting to the driving simulation lab, subjects will be asked to complete questionnaires. Sensors for monitoring heart rate (via ECG) and skin conductance will then be attached. For the ECG sensors, the skin will be cleaned with isopropyl alcohol and disposable electrodes (Vermed A10005) applied in a modified lead II configuration with the negative lead immediately under the right clavicle, the common immediately under the left clavicle, and the positive lead over the

